### STUDY PATIENT POPULATION

Liver transplant and cardiovascular surgery populations were chosen because they are the 2 patient populations which receive cryo during massive blood loss most frequently in the operating room. Although they don't have the same mechanisms of injury and coagulation dysregulation, they both are prone to severe and early hypofibrinogenemia, hyperfibrinolysis, thrombocytopenia, platelet dysfunction and dilutional coagulopathy during surgery. The CV surgery and liver transplant anesthesiology groups at Weill Cornell faithfully use ROTEM for real time goal directed blood product therapy. Other patient populations may receive cryo, but cryo tends to be less predictably used in these populations, less evidence based (i.e., less based on immediately available point of care coagulation lab results) and more of a last resort option, rather than an early planned intervention. The other groups of patients who require cryo are smaller, more heterogeneous and have more covariates that will make data analysis more difficult to interpret. Thus, the focus is on two fairly homogeneous patient groups at high probability to require cryo transfusion.

Inclusion criteria: Adult patients undergoing cardiovascular surgery or liver transplant who receive cryo during surgery during the two year study period. Cardiovascular surgery includes the following procedures: coronary artery bypass grafting, valve repair or replacement, open thoracic aortic and thoracoabdominal aortic surgery, atrial or ventricular septal defects, ventricular assist device implantation or revision, or any combination of the above.

### Exclusion criteria:

- 1) Patients who do not receive any cryo product in the OR.
- 2) Patients who are not cardiovascular surgery or liver transplant patients
- 3) Cardiac transplantation surgery
- 4) Patients who receive a product in error within either the cryo time period or the PR cryo time period. For example, PR cryo during a cryo month or cryo during a PR cryo time month.
- 5) Patients who receive less than 1 pool (5 units) of cryo
- 6) Pediatric patients (less than 18 years of age).
- 7) Patients who received both PR cryo and traditional cryo
- 8) Pregnant women

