### **SUMMARY**

Immediately replacing fibrinogen in perioperative bleeding patients with acquired fibrinogen deficiency improves outcomes. The product that is primarily used for fibrinogen replacement in the US, cryoprecipitate, must be stored frozen and expires six hours after thawing, resulting in a delay in transfusion of approximately 50 minutes from the time it is ordered, as well as unnecessary transfusion of more readily available but not indicated blood components that are transfused while the patients waits for cryo. A modified version of the product, pathogen reduced (PR) cryo, is now FDA approved and can be thawed and stored for 5 days, allowing the product to be available immediately when needed. No clinical studies are available for this product. In this quality improvement study, we will compare the effect that readily available, pre-thawed PR cryo has on transfusion practice in cardiovascular and liver transplant patients who receive PR cryo versus those who receive traditional cryo by randomizing cryo transfusions in the blood bank by month to all cryo or all PR cryo. All clinical decisions, including the need for cryoprecipitate, and laboratory testing will occur per standard of care.

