### **STUDY DESIGN**

Given that PR cryo can be more readily available for urgent perioperative need, the transfusion medicine service and anesthesiologists at NYP/WC would like to transition to this product. PR cryo is a more expensive product, so it is necessary to evaluate whether its availability will reduce the need for other blood products or reduce traditional cryo wastage, prior to fully converting to this product. A single center prospective, pilot cluster randomized study with an adaptive design will be used to compare the availability and cost effectiveness of cryo and PR cryo when it is ordered for standard clinical indications. In this design, the intervention and randomization are not made at the level of the individual patient, but rather on clusters of patients by month. The clusters will include all patients at NYP/WC for whom pooled cryo is ordered during a single month, not just liver transplant and cardiovascular surgery patients.

Since both products are considered clinically equivalent, the blood bank will alternate use of PR cryo and regular cryo each month for all patients with a cryo order over a one year period during the transition to the use of this new product. All patients will receive either traditional cryo or PR cryo in a given month; however, only a subset (CV and LT patients) will be studied.

Data from the EMR and lab systems will be collected from the NYP data warehouse during the one-year QA study and included in the data analysis. The following demographic variables will be collected: age, ethnicity, race, gender, underlying diseases, surgery type, medications given within 5 days of surgery.

The primary outcome will be the total number of blood components (RBCs, platelets, plasma) used over the admission within the first 30 days after surgery.

REDCap will be used for data collection/storage. Our data scientist, who is an Epic Clinical Data Navigator (CDN), will use SQL queries through the NYP Jupiter data warehouse for automated data extractions of clinical and laboratory data. A TRAC request will be submitted once the IRB is approved. Any variables not available through Jupiter will be extracted manually from the electronic medical record by the research coordinator and entered manually in REDCap. We will use the Safe Harbor method for de-identification of data. We will remove all 18 PHI elements referenced by HHS that could identify a patient.

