The secondary outcomes, which are all routinely available in the EMR per standard of care, will include:

1. Number of cryo or fibrinogen concentrate products used perioperatively (defined as anesthesia start time to 3 days post-procedure)

- 2. Number of RBC, plasma, and platelet products used perioperatively (defined as anesthesia start time to 3 days post-procedure)
- 3. Time from OR start time to start of cryo transfusion
- 4. Time from cryo order to start of transfusion
- 5. Number of cryo units wasted by blood bank per month during study periods.
- 6. Laboratory measures, as available in the medical record, related to the indications for cryo: pre and post transfusion FIBTEM amplitude at 10 mins and maximum clot firmness & fibrinogen level within 10 minutes to one hour after the end of the first cryo transfusion.
- 7. Highest and lowest fibrinogen level or ROTEM FIBTEM within 24 hours after surgery.
- 8. Volume in drains (e.g. chest tube for CV surgery) at 24 hours or until removed, whichever is sooner.
- Time from end of bypass pump until end of surgery (reflects time to hemostasis) for CV surgery
- 10. Length of stay (OR, ICU and hospital)
- 11. Need for ventilator
- 12. Time on ventilator
- 13. Overall cost of cryo vs PR cryo, when factoring wastage, during each 1-month period
- 14. Adverse events: fevers, infections, transfusion reactions within 5 days of surgery start time, need for surgical re-exploration, multiorgan system failure
- 15. Fibrinogen level most proximal to end of procedure

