if it is not properly accounted for in the analysis. This study will use randomization between intervention arms each month with a design known as the cluster randomized trial. This allows for the ability to assure that all research subjects in a given month will receive a particular cryo product and ensure the reduction in contamination of the two study arms (one of the primary reasons for designing studies in this fashion). In the planned trial, each month the Weill Cornell blood bank will be randomized to one of the two cryoprecipitates as part of a quality improvement study, the randomized product will be used as standard institutional policy for an entire calendar month. At the end of each month, the blood bank is re-randomized to a new standard policy that is used for the subsequent calendar month. This design is methodologically rigorous and tests the effect of a change in standard policy as it would actually be used in the clinical setting.

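### Patients are counted only if they receive cryo in the OR, which happens after the month's product is assigned and may depend on how quickly that product is available, so the arms may hold different patients.

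*Combined protocol and SAP*

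**What the plan says.** Assignment comes first. Under the rationale for a cluster randomized trial, "each month the Weill Cornell blood bank will be randomized to one of the two cryoprecipitates", and that product is used for the whole calendar month.

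Entry comes later. The inclusion criterion (Study Patient Population) is "Adult patients undergoing cardiovascular surgery or liver transplant who receive cryo during surgery". Exclusion 1 repeats this from the other side, "Patients who do not receive any cryo product in the OR", and exclusion 5 removes "Patients who receive less than 1 pool (5 units) of cryo".

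The two products differ by design in speed of access. The Summary describes conventional cryo as "resulting in a delay in transfusion of approximately 50 minutes from the time it is ordered", and PR cryo as pre-thawed, "allowing the product to be available immediately when needed". The statistical rationale adds that recipients are very hard to predict before surgery. The Consent section leaves the decision to transfuse to the clinicians.

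The primary analysis (Evaluation of Product Superiority) is an unadjusted two-sample t-test on logs, or a Wilcoxon test, described as intent-to-treat.

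**The concern.** Randomizing months balances the patients who come to surgery in each month. It does not by itself balance the subset who go on to receive cryo if the assigned product can influence who they are.

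In a conventional month, a patient's bleeding may stop, the operation may end, or another product may be given while cryo is thawing. That patient never receives cryo in the OR and drops out of the data. In a PR month the same patient could have received cryo at once and been counted. If such patients are milder bleeders, they lower the PR arm's mean count of RBCs, platelets and plasma without any component being saved.

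At stake is the comparison that will inform conversion to a more expensive product. Part of the 20% target could be met, or part of a real effect hidden, by a difference in who was counted. A larger sample would not remove this.

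**Working it through.** **1. The plan's own sample size.** Inputs from Sample Size Analysis: ratio of means 0.8, CV 1.1, 80% power, two-sided 5%, 251 per group.
- SD of logs = √ln(1 + 1.1²) = √ln 2.21 = 0.8905
- Log effect = |ln 0.8| = 0.2231
- n per group = 2 × [0.8905 × (1.960 + 0.842) / 0.2231]² = 250 (normal). A t-based calculation gives 251.
- Power at 251 per group is 80.2%.

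The stated figure reproduces. With the plan's design effect of about 1.01 it becomes 252 to 253, an immaterial difference.

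**2. Selection with no true product effect.** Suppose PR months admit a fraction x of extra recipients who would not have received cryo in a conventional month, and that these use r times the components of the others. The documents give neither x nor r; both are assumptions.
- Share of extras in the PR arm: s = x/(1 + x)
- Apparent geometric mean ratio: r^s
- PR-arm log variance: 0.8905² + s(1 − s)(ln r)²
- SE: the square root of the two arm variances, each divided by 251, added together
- Rejection rate: two-sided 5%, normal approximation, with z = s|ln r|/SE

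Worked case, x = 20%, r = 0.5: s = 0.2/1.2 = 0.1667. Log shift = 0.1667 × 0.6931 = 0.1155, so the ratio is 0.891. PR-arm SD = 0.927 and SE = 0.0811. Then z = 1.42 and the rejection rate is 29.6%. The shift is 0.1155/0.2231 = 52% of the target on the log scale.

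| Extra recipients x | Relative use r | Apparent ratio | Rejection rate |
|---|---|---|---|
| 2% | 0.5 | 0.99 | 5.3% |
| 10% | 0.8 | 0.98 | 5.7% |
| 5% | 0.5 | 0.97 | 7% |
| 10% | 0.5 | 0.94 | 12% |
| 20% | 0.6 | 0.92 | 19% |
| 20% | 0.5 | 0.89 | 30% |
| 20% | 0.4 | 0.86 | 46% |

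The range runs from essentially nominal alpha to serious distortion. The table covers one direction only; selection towards milder patients in conventional months would act against PR cryo in the same way.

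**3. What the planned outputs would show.** MELD and EUROSCORE describe risk before surgery, not bleeding during it. Pre-transfusion FIBTEM (secondary outcome 6) and time from OR start to cryo (item 3 of the Study Design list) would respond to a change in who receives cryo, but only among recipients. The plan calls for no count, by arm or month, of eligible operations, of orders, or of patients removed under exclusions 1 and 5.

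**The case against.** The strongest reply is that cryo use here follows an algorithm. Study Patient Population says both anesthesiology groups consistently use ROTEM to direct therapy, and Laboratory Testing says a ROTEM algorithm is in place for both surgery types. That may keep the recipients similar across months. It does not remove the wait between order and transfusion, so the effect may be limited but is not excluded.

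Nor is the plan without any check: pre-transfusion FIBTEM, time to cryo and the optional covariate models are partial diagnostics. FIBTEM is collected only as available, and none of them supplies a denominator.

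A reader might infer several stronger claims that the documents do not support:
- **That the bias must favour PR cryo.** Anticipatory ordering in conventional months could bring milder patients into that arm, and deaths before cryo arrives could also act the other way.
- **That clinicians know which product they are giving.** The documents are silent on blinding.
- **That fibrinogen concentrate is a routine alternative at the site.** This rests only on an outcome label, "Number of cryo or fibrinogen concentrate products used perioperatively".
- **That Study Design sets a competing eligibility rule.** "The clusters will include all patients at NYP/WC for whom pooled cryo is ordered during a single month" describes whom the monthly policy covers; the same section says that only a subset is studied.

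Exclusion 5 adds little, because the product is supplied as pools.

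**Conclusion.** The structural point stands: entry depends on an event after assignment that the availability difference can affect. The set analysed as intent-to-treat is therefore selected after randomization. Confidence is high on the structure and low on size and direction.

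With no true effect, the plan's CV and 251 per arm, the illustration runs from a ratio of about 0.97 with 7% rejection (5% extra recipients at half use) to 0.89 with about 30% rejection (20% extra at half use). Smaller assumptions leave the test close to 5%. These figures show what selection could do. They do not show that it will occur, and they do not support saying that a 20% reduction would be an artefact.

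**What to change.** 1. **Count the denominator.** From the warehouse query already planned, extract all adults with a listed cardiovascular procedure or liver transplant in each study month. Report by arm and month the number eligible, with cryo ordered in the OR, given cryo, and excluded under items 1 and 5, alongside pre-transfusion FIBTEM.
2. **Prespecify a supportive analysis** of the primary outcome in all these operations by the month's assigned product. Use a count model or rank test, because some patients will have zero components and the log t-test cannot take zeros, and account for month. State that a reduction among recipients will not be attributed to PR cryo without qualification if the proportions given cryo differ between arms, and say in advance what difference counts.
3. **Add a sensitivity set** that keeps patients with an OR cryo order but no transfusion. This recovers patients overtaken by the wait. It is not a full cure, because an order also follows assignment and can respond to availability.

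The cost is wider data extraction, some of it manual where the warehouse lacks a variable; no patient procedures are added. The supportive analysis may be heavily diluted. If the effect exists only in a share p of operations that receive cryo, n per group is roughly 250/p²: 445 at 75%, 1,000 at 50% and 4,000 at 25%. The documents do not give p, and the same log SD is assumed, so these are indicative only. The analysis should be read for consistency with the primary result, not as a second powered test.

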#### **SAMPLE SIZE ANALYSIS**

The primary endpoint of the study is total number of blood components other than cryo (RBCs, platelets, plasma) used over the hospital admission within the first 30 days after surgery. The goal of the trial is to demonstrate a 20% reduction in this total blood product use for PR cryo compared to the total observed with conventional cryo. In order to determine this effect size and the patient variability associated with this outcome, data were collected from 150 cardiovascular surgery and liver transplant cases at the study center during 6 months in 2021. Because the number of units used was clearly right-skewed and, therefore, possibly lognormally distributed, the sample size determination was based on the hypothesized ratio of means (effect size) of 0.8. In addition, the coefficient of variation is the key determinant of variability with log-normal data, and this was seen with the recent data to be a value of 1.1. The other issue to consider in this calculation is the cluster randomization. However, the cluster in this study is the month when the surgery is performed. The assumption is made that the intracluster correlation of the primary outcome within a given month should be very small, say 0.0001. As a result, this would have very little effect on the sample size (the Kish design effect is about 1.01 assuming approximately 100 subjects per month). Then with 80% power and 5% significance (two-sided), the number of subjects per group would be 251.

However, there is a possibility that the effect size has been overestimated. Thus, a sample size re-estimation will be conducted after 60% of the subjects have been included in the trial. The method of Gould (Gould AL. Interim analyses for monitoring clinical trials that do not materially affect the type I error rate. Stat Med 1992; 11:55-66.) will be used to re-evaluate the sample size.

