#### **EVALUATION OF PRODUCT SUPERIORITY**

The primary outcome of total number of blood components (RBCs, platelets, plasma) used over the admission within the first 30 days after surgery will be evaluated using a two-sample t-test on the log-transformed values or the Wilcoxon rank-sum test if the log-transform does not result in an acceptable comparability to a normal distribution. This will be based on an intent-to-treat paradigm (all subjects randomized will be evaluated and in the group they were randomized to). However, it is assumed that all of the subjects will be appropriately evaluated for this endpoint.

There are a number of secondary endpoints, and the specific statistical method is indicated below:

- 1. Number of cryo or fibrinogen concentrate products used perioperatively (defined as anesthesia start to 24 hours post-procedure): Wilcoxon rank-sum test
- 2. Number of RBC, plasma, and platelet products used perioperatively (defined as anesthesia start to 24 hours post-procedure): Wilcoxon rank-sum test
- 3. Time from cryo order to ready in the blood bank: Wilcoxon rank-sum test
- 4. Time from cryo order to start of infusion: Wilcoxon rank-sum test
- 5. Number of cryo units wasted by blood bank per day during study periods: Wilcoxon rank-sum test
- 6. Laboratory measures for cryo and PR cryo (pre and post transfusion FIBTEM amplitude at 10 mins and maximum clot firmness, fibrinogen): Wilcoxon rank-sum test
- 7. Volume in mediastinal drains (e.g. chest tube for CV surgery) at 24 hours (or until removed): Wilcoxon rank-sum test
- 8. Length of stay (OR, ICU and hospital) & time on ventilator: log-rank test, particularly if there is any censoring
- 9. Overall cost of cryo vs PR cryo, when factoring wastage, during each 1-month period: Wilcoxon rank-sum test
- 10. Fibrinogen level most proximal to end of procedure, with adjustment for fibrinogen dose administered (if known): without adjustment the Wilcoxon rank-sum test can be used; with adjustment a properly selected linear model (depending on the link function required)

[figure not shown]
In order to control statistical significance for this number of endpoints, the Holm procedure will be used.

[figure not shown]
Many of the endpoints noted above can be evaluated after adjustment with selected covariates using a properly selected linear model (depending on the link function required).

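### Exclusion 5 can remove a patient because a transfusion reaction stopped the only pool, and no safety population is defined to keep that patient in the adverse event comparison

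*Combined protocol and SAP*

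**What the plan says.** Study Patient Population includes adults having cardiovascular surgery or liver transplant "who receive cryo during surgery during the two year study period". The Exclusion criteria then narrow this group by what was actually given. Item 1 removes patients with no cryo in the operating room, and item 5 removes "Patients who receive less than 1 pool (5 units) of cryo". Item 5 makes no exception for a transfusion that was begun and stopped, and the documents do not say whether *receive* means issued, started or fully infused.

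Secondary outcome 14 in Study Design reads "Adverse events: fevers, infections, transfusion reactions within 5 days of surgery start time, need for surgical re-exploration, multiorgan system failure". Evaluation of Product Superiority states an intent-to-treat principle, "all subjects randomized will be evaluated and in the group they were randomized to", in its paragraph on the primary outcome. Its list of secondary analyses gives neither a method nor an analysis set for adverse events, and no safety population is defined elsewhere.

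Product is assigned by month. The Rationale for a Cluster Randomized Trial says that "the randomized product will be used as standard institutional policy for an entire calendar month".

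**The concern.** The month fixes the product before any patient is transfused, so item 5 acts after assignment and after exposure. Because item 1 already removes patients with no cryo, item 5 adds only those with some cryo but less than one pool in total. One direct way into that group is a pool stopped because the patient reacted to it. Eligibility would then depend on an event that the trial intends to count.

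The Summary says of pathogen-reduced cryo that "No clinical studies are available for this product", and Study Design presents the trial as a step before full conversion to the product. Its reaction count would therefore be read as early clinical information on safety, even though the main aims are availability and cost. Reactions are probably few, so losing even a few cases could change the count materially.

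**Working it through.** **1. The plan's own sample size.** Sample Size Analysis gives the "hypothesized ratio of means (effect size) of 0.8", says of the coefficient of variation that "this was seen with the recent data to be a value of 1.1", and uses 80% power, a two-sided 5% level and an intracluster correlation of 0.0001 with about 100 subjects per month.

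- Log-scale difference: |ln 0.8| = 0.2231.
- Log-scale SD: √ln(1 + 1.1²) = 0.8905.
- Normal approximation: n = 2 × [0.8905 × (1.960 + 0.842) / 0.2231]² = 250 per group. The noncentral t gives 251.
- Design effect: 1 + 99 × 0.0001 = 1.0099, and 250 × 1.0099 = 252.5.

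The stated 251 per group is reproduced, and this point does not dispute it.

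**2. How many reaction cases could be lost.** The documents give neither a reaction rate nor the share of pools stopped early, so both are assumed. Let r be the true reaction rate and f the share of reaction cases that never reach one pool in total. Cases lost per arm = 251 × r × f.

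- Low end: 251 × 1% × 10% = 0.25.
- High end: 251 × 5% × 50% = 6.3.

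**3. What the tables would show.** Lost patients leave both numerator and denominator, so the observed rate is r(1 − f) / (1 − rf). An assumed true rate of 2% appears as 1.8% (f = 10%), 1.5% (f = 25%) or 1.0% (f = 50%). For an assumed true comparison of 4% v 1%:

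| Share lost, same in both arms | Observed rates | Difference | Ratio |
|---|---|---|---|
| 0% | 4.00% v 1.00% | 3.0 points | 4.0 |
| 25% | 3.03% v 0.75% | 2.3 points | 4.0 |
| 50% | 2.04% v 0.50% | 1.5 points | 4.1 |

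With equal loss the absolute difference shrinks and the ratio hardly moves. With unequal loss the ratio moves too: 50% lost in the 4% arm and 25% in the 1% arm gives 2.04% v 0.75%, a ratio of 2.7.

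**4. Effect on the primary endpoint.** Power = Φ[0.2231 / (0.8905 × √(2/n)) − 1.960]. It is 80.2% at n = 251 and 79.4% at n = 246, that is, with 5 patients lost per arm.

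**The case against.** The best counter-argument is that item 5 may not work this way in practice. Its threshold is in product units, the data come from warehouse queries, and cryo use is counted in products. No infused cryo volume is named as a variable. A started pool could be recorded as one pool, and the patient would stay in. That is possible, but nothing in the documents says so, and the ordinary sense of receiving less than one pool includes a part-infused pool. The ambiguity itself needs settling.

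Several limits on the size of the problem stand:

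- Item 5 concerns total cryo. A patient whose first pool is stopped but who later reaches one pool in total is not caught.
- Equal proportional loss leaves the risk ratio almost unchanged, as the table shows.
- The trial is described as a quality improvement study of availability and cost, and no test of adverse events is listed.

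A reader might also infer three stronger points that the documents do not support:

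- *That the reaction table would be emptied to 0 v 0.* This follows only if the sole reactions counted are those that stop a pool and every such patient is lost. Outcome 14 also covers reactions that do not stop a pool and several other kinds of event.
- *That a death during the first pool is a lost adverse event.* Death is not listed in outcome 14. Such a patient could drop out of the analysis set, but no counted death event is lost.
- *That item 5 seriously undermines the intent-to-treat analysis.* The sentence concerns the primary outcome, items 4 and 7 (product given in error, both products given) conflict with it more directly, and the loss of power is trivial.

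**Conclusion.** The point holds in a limited form. On its plain wording, item 5 can remove a patient because of a listed outcome, and no safety set keeps that patient in. The result is understated reaction rates and an understated absolute difference, with a distorted ratio if early stopping differs by product.

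The size cannot be determined from the documents. Under the assumed values, 0.25 to 6.3 cases per arm are lost, and a 3.0-point difference appears as 2.3 to 1.5 points when 25% to 50% of cases are lost. These figures rest on assumed rates, on reading *receive* as volume infused, and on the affected patients not reaching one pool later. The primary endpoint and the 251 per group are not materially affected.

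**What to change.** Three changes to the text are enough:

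1. For adverse events, do not apply item 5. Define the safety population as every otherwise eligible cardiovascular or liver transplant patient in whom transfusion of either product was started, whatever volume was given, analysed by the month's assigned product.
2. Report the number of transfusions stopped early, by product.
3. State that *receive* in item 5 means a pool started, not completed.

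A threshold on the amount ordered would not be a good substitute for item 5. Ordering also happens after the month is assigned and could itself respond to the ready availability of pathogen-reduced cryo.

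The start of cryo transfusion is already needed for secondary outcomes 3 and 4, so the safety set needs no new data source. The sample size does not change. The cost is a few sentences and a handful more patients with partial exposure in the safety tables.
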